10.6.2. Study Population

Demographics
Age

 • GSK standard IDSL algorithms will be used for calculating age where birth date will be imputed as follows: 
 ○ Any participant with a missing day will have this imputed as day ‘15’. ○ Any participant with a missing date and month will have this imputed as ‘30th June’. • Birth date will be presented in listings as ‘YYYY’. • Age will be calculated based on the screening visit date. • Age group categories are 18-64, 65-74, 75-84
Body Mass Index (BMI)

 • Calculated as Weight (kg) / [Height (m)²]

Baseline Characteristics
Smoking Status

 If the last smoked date (SUSMLSDT) is missing and a partial date (SUSMLSD) is not missing, then the following imputation should be applied to the partial smoking date for use in the reclassification of smoking status calculation: 
 '01' will be used for the day and 'Jan' will be used for the month. Former smokers will be reclassified as current smokers if screening date – last smoked date < 183 days.
COPD Exacerbation (Historical) Categories

 Moderate/severe historical exacerbations are defined as those requiring oral/systemic corticosteroids and/or antibiotics or hospitalisation. The number of exacerbations requiring oral/systemic corticosteroids and/or antibiotics, the number requiring hospitalisation and the number of moderate/severe COPD exacerbations for each participant will be categorized as 0, 1, ≥2 for summary displays.
GOLD Grade 1-4 at Screening

 Participants will be classified into Global Initiative on Obstructive Lung Disease (GOLD) Grades 1-4 using the post-bronchodilator percent predicted FEV₁ assessment at Screening: 
 GOLD Grade 1 (Mild): percent predicted FEV₁ ≥80% GOLD Grade 2 (Moderate): 50% ≤ percent predicted FEV₁ <80% GOLD Grade 3 (Severe): 30% ≤ percent predicted FEV₁ <50% GOLD Grade 4 (Very Severe): percent predicted FEV₁ <30%
GOLD Grade A-D at Screening

 Participants will be classified into GOLD Grades A-D definitions as follows: 
 A. Low risk, less symptoms: baseline CAT < 10 AND GOLD Grade 1-2 AND ≤1 exacerbation; (no hospitalizations for exacerbations), prior year. B. Low risk, more symptoms: baseline CAT ≥ 10 AND GOLD Grade 1-2 AND ≤1 exacerbation (no hospitalizations for exacerbations), prior year C. High risk, less symptoms: baseline CAT < 10 AND either GOLD Grade 3-4 OR ≥ 2 exacerbations, prior year OR ≥1 exacerbation leading to hospitalization, prior year D. High risk, more symptoms: baseline CAT ≥ 10 AND either GOLD Grade 3-4 OR ≥ 2 exacerbations, prior year OR ≥1 exacerbation leading to hospitalization, prior year

Concomitant Medications
Respiratory Medication Class

 COPD concomitant medications will be grouped into the following RMCs based on pre-defined code lists derived from ATC classifications: 
 Androgens and Estrogens Anti-IgE, Anti-IL5 Anticholinergic Antiinfectives (antibiotics, antiseptics only) Antimycotics Antivirals Beta 2 Agonist Corticosteroid – Inhaled Corticosteroid – Depot Corticosteroid – Systemic, oral, parenteral and intra-articular Corticosteroid – Other Leukotriene Receptor Antagonist Long-acting anticholinergic

 ○ Long-acting beta-2 agonist ○ Mucolytics ○ Nedocromil or Cromolyn Sodium ○ Oxygen ○ PDE4 Inhibitors ○ Short-acting anticholinergic ○ Short-acting beta-2 agonist ○ Xanthine ○ Other medication given for exacerbation ○ Other COPD medication
COPD Medication Combination

 ● COPD medications will be summarized at the following time points: 
 ○ At Screening: Taken on the day of the Screening visit excluding medications that stopped on the day of the Screening visit ● Medication combinations of all RMC categories will be derived. Medications will be summarized based on individual and combinations of the following RMC categories, with or without other medications: 
 ○ ICS ○ LABA ○ LAMA ○ Xanthine ○ PDE4 inhibitor ○ Anti-IgE, Anti-IL5

Exposure
Exposure to Study Treatment

Duration of exposure to study treatment is calculated as (treatment stop date – treatment start date +1).
 
The following exposure categories will be derived: ≥1 day, ≥2 weeks, ≥4 weeks, ≥8 weeks, ≥12 weeks, ≥16 weeks, ≥20 weeks, ≥ 24 weeks, ≥32 weeks, ≥40 weeks and ≥52 weeks.

10.6.3. Efficacy

SGRQ
SGRQ-C Total and Domain Scores

 ● The SGRQ-C contains 40 questions grouped into three domains (Symptoms, Activity and Impacts). ● Details for how to score the SGRQ-C, including handling of missing data or multiple responses to questions, are outlined in the SGRQ-C manual (Jones, 2016). ● SGRQ-C total and domains scores will be converted to SGRQ scores as described in the manual. ● Changes from baseline in total and domain scores will be calculated for the converted scores. ● If the language of the SGRQ-C conducted at a post-baseline visit is different to the language used at baseline, all SGRQ scores at that visit and all subsequent visits will be set to missing.

CAT
CAT Score

 ● The CAT consists of eight items each formatted as a six-point differential scale: 0 (no impact) to 5 (high

- impact). A CAT score will be calculated by summing the non-missing scores on the eight items. The score can have values ranging from 0 to 40.
- If one item is missing, then the score for that item is set as the average of the non-missing items. If more than one item is missing, then the CAT score will be set to missing.
 - If the language of the CAT conducted at a post-baseline visit is different to the language used at baseline, the CAT score for that visit and all subsequent visits will be set to missing.
 - If there is more than one response to a question at a visit or duplicate questionnaires, the CAT score for that visit will be set to missing.

Rescue Medication Use

Daily eDiary

- Participants were instructed to complete the daily eDiary in the evening (typically at bedtime) to collect the number of puffs of rescue medication(s) over each 24-hour period.
- The table below shows which daily rescue medication use records are to be used to calculate summaries for each period. Any daily rescue medication use data collected after the minimum of (Day 364 or the day before study treatment stop date) will not be slotted.

Period	First day	Last day
Baseline [1]	Day -7	Day -1
Weeks 1 – 4 ^[1]	Day 1	Day 28
Weeks 5 – 8 ^[1]	Day 29	Day 56
Weeks 9 – 12 ^[1]	Day 57	Day 84
Weeks 13 – 16 ^[1]	Day 85	Day 112
Weeks 17 – 20 ^[1]	Day 113	Day 140
Weeks 21 – 24 ^[1]	Day 141	Day 168
Weeks 25 – 28 ^[1]	Day 169	Day 196
Weeks 29 – 32 ^[1]	Day 197	Day 224
Weeks 33 – 36 ^[1]	Day 225	Day 252
Weeks 37 – 40 ^[1]	Day 253	Day 280
Weeks 41 – 44 ^[1]	Day 281	Day 308
Weeks 45 – 48 ^[1]	Day 309	Day 336
Weeks 49 – 52 ^[1]	Day 337	Earliest of (Study day 364 and day before study treatment stop date)

[1] The denominator for baseline and 4-week mean scores is the number of days with a non-missing score; this is also used to determine whether a baseline (>=4 days) or 4-week mean (>=10 days) is calculated or not.

- If a participant has more than one daily diary record for any given day, the worst-case response on that day for each endpoint will be used in the summaries and analyses. i.e. the maximum number of puffs of rescue use reported will be counted for the day in question and used to determine if it was a rescue-free day.
- A rescue-free day is defined as a day where the total puffs is 0.
- For each summary period, the mean number of puffs per day and the percentage of rescue free days, will be calculated, using the number of days with non-missing values for the endpoint as denominator.
- Rescue use will be summarized over the periods defined above.

Metered Dose Inhaler (MDI) Sensor

- The MDI Sensor will be attached to the participant’s rescue medication(s). The MDI Sensor will transmit its medication use data to the LogPad provided by ERT via a Bluetooth connection.

- The mean number of occasions of rescue per day and the percentage of rescue-free days will be calculated over the same time periods and using the same assumptions as rescue use via diary.
- Rescue-free Days - days within the diary data collection period with no recorded rescue inhaler usage by the sensor will be assigned a rescue inhaler usage of 0.

10.6.4. Safety

Adverse Events
AEs of Special Interest

 • AESI are defined as events in the 'Infective pneumonia' SMQ in the MedDRA version current at the time of reporting.

Maximum/Minimum Post-Baseline and Worst-Case Post-Baseline	
Definition	Reporting Details
Maximum post-baseline (QTcF, QTcB, PR interval, ECG heart rate, pulse rate, systolic BP, diastolic BP and laboratory tests)	Change from baseline of maximum value over all time-points after Day 1
Minimum post-baseline (Diastolic BP and laboratory tests that do not have a lower limit = 0)	Change from baseline of minimum value over all time-points after Day 1
Worst case post-baseline (ECG findings)	
 • 'Abnormal' if any on-treatment assessment is evaluated as 'Abnormal' • 'Unable to evaluate' if all on-treatment assessments are 'Unable to evaluate' • 'Normal' if any on-treatment assessment is evaluated as 'Normal' and there are no on-treatment assessments evaluated as 'Abnormal'

NOTES:

- The treatment phase definitions specified in Section 10.4.1 will be used and only assessments within the on-treatment period will be considered in assessment of minimum/maximum/worst-case post-baseline.
- Assessment of minimum/maximum/worst-case post-baseline will include on-treatment data from scheduled, unscheduled and study treatment discontinuation visits (if applicable)

Laboratory Parameters
General

 • NQ laboratory results will be treated as missing in summary displays. However, the results will be listed as received (e.g. '<x' or '>x'). • A 'worst case post-baseline' change classification will be derived, in which participants will be counted in the 'to low' and 'to high' categories if they reported a change from an 'in range' baseline to a value below or above the PCI criteria (respectively) at any scheduled or unscheduled on-treatment visit. Participants who did not report a change to a value outside the PCI criteria at any visit after the start of study treatment will be counted in the 'to w/in range or no change' category.
Multiple Measurements for On-Treatment Visits for Safety

Laboratory Parameters
General

 Participants having both high and low values relative to PCI criteria at post-baseline visits for safety parameters will be counted in both the high and low categories of the “worst case post-baseline” row of related summary tables.

ECG
General

 The QTc data was collected via machine derived values (QTCB/QTCF) or manually derived values (QTCBC/QTCFC). For the purposes of reporting the following variable should be combined: 
 Combine QTCF with QTCFC If both QTCF and QTCFC are missing (and QT and RR are non-missing, then the QTcF interval will be derived as follows: 
 $QTcF \text{ interval (msec)} = QT / [(RR/1000)^{(1/3)}]$ If RR interval is not collected and the corrected QT interval by Bazett’s method (QTcB) is collected, then RR interval (msec) will be derived prior to deriving QTcF as follows: $RR \text{ interval (msec)} = 1000 * [(QT/QTcB)^2]$ If QTcF intervals are collected they will not be rederived.

ECG Categories
 Maximum and maximum increase in QTcF values will be reported in categories as below. In participants who have QTc above 450 at baseline, decreases that result in a QTc that remains above 450 will be considered No Change.

ECG Parameter	Units	Category
Absolute		
Absolute QTcF Interval	msec	No Change or Decrease to <=450
		Increase To >450 to <=480
		Increase To >480 to <=500
		Increase To >500
Change from Baseline		
Change from Baseline QTcF	msec	Increase of <=30 msec
		Increase of 31-60 msec
		Increase of >60 msec

Assessment of maximum post-baseline will include on-treatment data from scheduled, unscheduled and study treatment discontinuation visits (if applicable)

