10.8. Appendix 8: Values of Potential Clinical Importance

10.8.1. Laboratory Values

The following table identifies a range of potential clinical importance (PCI) for each laboratory analyte. Limits with an 'x' are multipliers of the central laboratory normal range. Values above and below this range will be considered of PCI.

Haematology Analyte (units)	Effect	COPD Patients	
		Low	High
Platelet Count (x10 ⁹ /L)		0.90x	1.10x
Red Blood Cell Count (x10 ¹² /L)		0.93x	1.07x
White Blood Cell Count (x10 ⁹ /L)		0.70x	1.60x
Reticulocyte Count (%)			>4%
Haemoglobin (g/L)	Males	0.85x	1.20x
	Females	0.85x	1.20x
Hematocrit (Ratio of 1)	Males	0.50x	1.30x
	Females	0.50x	1.30x
MCV (fL)		0.25x	2.00x
MCH (pg)		0.85x	1.20x
MCHC (g/dL)		0.85x	1.10x
Neutrophils (%)		0.65x	1.50x
Lymphocytes (%)		0.80x	1.20x
Monocytes (%)		0.80x	1.60x
Eosinophils (%)			2.00x
Basophils (%)			5.00x

Note: Multipliers are identified by "x", otherwise actual comparison values are provided with units.

Chemistry Analyte	Effect	COPD Patients	
		Low	High
BUN (mmol/L)		0.70x	1.60x
Creatinine (μmol/L)			1.30x (or >27 μmol/L increase from baseline)
Glucose fasting (mmol/L)		<0.6x	>4x
Sodium (mmol/L)		0.80x	1.15x
Potassium (mmol/L)		0.75x	1.30x
Chloride (mmol/L)		0.90x	1.10x
Bicarbonate (mmol/L)		<18 mmol/L	>32 mmol/L
Calcium (mmol/L)		0.85x	1.08x
GGT (U/L)		0.85x	1.10x
Uric Acid (mg/dL)	Males	<2.1 mg/dL	>8.5 mg/dL
	Females	<2.0 mg/dL	>7.0 mg/dL
Albumin (mmol/L)		0.90x	1.50x
Total Protein (mg/dL)			1.25x

Note: Multipliers are identified by “x”, otherwise actual comparison values are provided with units.

Liver Function Test Analyte	Effect	PCI Range	Unit
ALT/SGPT	High	≥ 3x ULN	U/L
AST/SGOT	High	≥ 3x ULN	U/L
Alkaline Phosphatase	High	≥ 2x ULN	U/L
Total Bilirubin	High	≥ 2x ULN	μmol/L
Direct Bilirubin	High	≥ 2x ULN	μmol/L
Total Bilirubin + ALT	High	≥ 2x ULN Total Bilirubin + ≥ 3x ULN ALT	μmol/L U/L

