10.10.5. Safety Tables

Safety: Tables					
No.	Population	IDSL / Example Shell	Title	Programming Notes	Deliverable [Priority]
Adverse Events (AEs)					
3.1.	Safety	AE3	Summary of All Adverse Events by Preferred Term	ICH E3	SAC
3.2.	Safety	AE3	Summary of Common (>=5%) Adverse Events by Overall Frequency	ICH E3	SAC
3.3.	Safety	AE3	Summary All Drug-Related Adverse Events by Preferred Term	ICH E3	SAC
3.4.	Safety	AE15	Summary of Common (>=5%) Non-serious Adverse Events by Preferred Term (Number of Subjects and Occurrences)	FDAAA, EudraCT	SAC
Serious and Other Significant Adverse Events					
3.5.	Safety	AE16	Summary/Listing of Serious Adverse Events by Preferred Term [Number of Subjects and Occurrences]	FDAAA, EudraCT	SAC
3.6.	Safety	AE3	Summary of Pre-treatment Serious Adverse Events by Preferred Term		SAC
3.7.	Safety	AE3	Summary of On-treatment Serious Adverse Events by Preferred Term		SAC
3.8.	Safety	AE3	Summary/Listing of Adverse Events Leading to Permanent Discontinuation of Study Treatment or Withdrawal from Study by Preferred Term	IDSL	SAC
3.9.	Safety		Summary/Listing of On-treatment Adverse Events of Special Interest		SAC
Laboratory: Chemistry					

Safety: Tables					
No.	Population	IDSL / Example Shell	Title	Programming Notes	Deliverable [Priority]
3.10.	Safety	LB1	Summary of Chemistry Changes from Baseline	ICH E3	SAC
3.11.	Safety	LB17	Summary/Listing of Worst Case Chemistry Results by Potential Clinical Importance Criteria (Post-Baseline Relative to Baseline)	ICH E3	SAC
Laboratory: Haematology					
3.12.	Safety	LB1	Summary of Haematology Changes from Baseline	ICH E3	SAC
3.13.	Safety	LB17	Summary/Listing of Worst Case Haematology Results by Potential Clinical Importance Criteria (Post-Baseline Relative to Baseline)	ICH E3	SAC
Laboratory: Hepatobiliary (Liver)					
3.14.	Safety	LIVER1	Summary of Liver Monitoring/Stopping Event Reporting	IDSL	SAC
3.15.	Safety	LIVER10	Summary/Listing of Hepatobiliary Laboratory Abnormalities	IDSL	SAC
ECG					
3.16.	Safety	EG1	Summary of ECG Findings	IDSL	SAC
3.17.	Safety	EG10	Summary/Listing of Maximum QTc Values Post-Baseline Relative to Baseline by Category	IDSL	SAC
3.18.	Safety	EG2	Summary of Change from Baseline in ECG Values by Visit	IDSL	SAC
3.19.	Safety	EG11	Summary/Listing of Maximum Increase in QTc Values Post-Baseline Relative to Baseline by Category	IDSL	SAC
Vital Signs					

Safety: Tables					
No.	Population	IDSL / Example Shell	Title	Programming Notes	Deliverable [Priority]

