24.	Safety	MH2	Listing of Medical Conditions for Subjects with Liver Stopping Events	IDSL	SAC
25.	Safety	SU2	Listing of Substance Use for Subjects with Liver Stopping Events	IDSL	SAC
All Laboratory					
26.	Safety	LB5	Listing of Chemistry Data for Subjects with Any Value of Potential Clinical Importance	ICH E3	SAC
27.	Safety	LB5	Listing of Haematology Data for Subjects with Any Value of Potential Clinical Importance	ICH E3	SAC
28.	Safety	LB5	Listing of Chemistry Values of Potential Clinical Importance		SAC
29.	Safety	LB5	Listing of Haematology Values of Potential Clinical Importance		SAC
30.	Safety	LB14	Listing of Chemistry Data with Character Results		SAC
31.	Safety	LB14	Listing of Haematology Data with Character Results		SAC
ECG					
32.	Safety	EG3	Listing of All ECG Values for Subjects with Any Value of Potential Clinical Importance	IDSL	SAC
33.	Safety	EG3	Listing of ECG Values of Potential Clinical Importance	IDSL	SAC
34.	Safety	EG5	Listing of All ECG Findings for Subjects with an Abnormal ECG Finding	IDSL	SAC

ICH: Listings					
No.	Population	IDSL / Example Shell	Title	Programming Notes	Deliverable [Priority]
35.	Safety	EG5	Listing of Abnormal ECG Findings	IDSL	SAC
Vital Signs					
36.	Safety	VS4	Listing of All Vital Signs Data for Subjects with Any Value of Potential Clinical Importance	IDSL	SAC
37.	Safety	VS4	Listing of Vital Signs of Potential Clinical Importance	IDSL	SAC

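### Off-scale (NQ) laboratory results are set to missing without exempting the worst-case PCI classification, so a certain PCI value can be counted as no change in Tables 3.11 and 3.13

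*SAP*

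**What the plan says.** Three adjoining rules matter.

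- **NQ rule (Section 10.6.4, Laboratory Parameters).** "NQ laboratory results will be treated as missing in summary displays". The sentence after it keeps these results in listings as received and shows that both '<x' and '>x' are meant. The abbreviations list expands NQ as non-quantifiable.
- **Worst-case classification (next bullet, same section).** A participant goes to 'to low' or 'to high' after moving from an in-range baseline to a value beyond the PCI criteria at any scheduled or unscheduled on-treatment visit. The remaining category, within range or no change, takes "Participants who did not report a change to a value outside the PCI criteria at any visit after the start of study treatment".
- **PCI limits (Section 10.8.1).** They are multiples of the central laboratory normal range or absolute figures. "Values above and below this range will be considered of PCI".

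The displays by these criteria are Table 3.11, "Summary/Listing of Worst Case Chemistry Results by Potential Clinical Importance Criteria", and Table 3.13, "Summary/Listing of Worst Case Haematology Results by Potential Clinical Importance Criteria" (Section 10.10.5). Section 5.2 defines baseline as the most recent non-missing pre-dose assessment; for clinical laboratory data both Screening and Day 1 count.

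**The concern.** An off-scale result is often not uninformative about PCI status. If the reported bound is already past the limit, the true value is certainly past it. The NQ rule discards that information, and the next bullet then places the participant in the no-change category, because no out-of-PCI value remains. The bullet has no exemption for NQ results, and no outcome for a participant with nothing left to evaluate. The general derivation rules (10.6.1), missing-data rules (10.7.2), reporting standards (10.5.2) and PCI appendix (10.8.1) do not restore these results.

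Section 2.1 gives safety as the primary interest of the report. Tables 3.11 and 3.13 exist to show PCI shifts, and as written they can report a certain shift as none.

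**Working it through.** The SAP states no figure to reproduce, so the check applies the rules literally and then counts their reach.

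**1. When does a bound settle PCI status?** A result '>x' is certainly high if x is at or above the upper limit. A result '<x' is certainly low if x is at or below the lower limit.

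**2. Literal classification.** Take the platelet multipliers in Section 10.8.1 (0.90x and 1.10x) with an assumed normal range of 100 to 200. The limits are 0.90 × 100 = 90 and 1.10 × 200 = 220. With an in-range baseline:

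| On-treatment results | As written | Using the bound |
|---|---|---|
| '<50', 150 | no change | to low |
| '>400', 150 | no change | to high |
| '<50' only | no change | to low |
| '<50', 80 | to low | to low |
| '<95', 150 | no change | no change |

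The last two rows mark the limits of the point. A quantified value beyond the same limit rescues the count, and a bound that does not reach the limit proves nothing.

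Bicarbonate has absolute limits, below 18 and above 32 mmol/L. A miscount needs '<x' with x of 18 or less, or '>x' with x of 32 or more. With an assumed assay range of 10 to 40, both '<10' and '>40' would be certain PCI values counted as no change.

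**3. Analytes exposed (Section 10.8.1).**

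| | Analytes | High limit | Low limit | No low limit |
|---|---|---|---|---|
| Haematology | 14 | 14 | 11 | reticulocytes, eosinophils, basophils |
| Chemistry | 12 | 12 | 10 | creatinine, total protein |
| Total | 26 | 26 | 21 | 5 |

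These are ceilings: a limit may exist that no off-scale result can reach. Neutrophils are a percentage with a high limit of 1.50x, so if the upper normal exceeds 100 / 1.50 = 66.7% (the SAP does not give it), the limit lies above 100%.

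**4. Weight of one miscount.** The change in a category is 100/n percentage points. With the planned 50 per arm (Section 2.3), 100/50 = 2.0. The SAP gives no treated number, so smaller arms are assumptions: 100/25 = 4.0, 100/20 = 5.0, 100/10 = 10.0.

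**5. Direction.** Dropping a post-baseline off-scale result can only remove a shift. Baseline differs. If an off-scale Day 1 result is treated as missing, Section 5.2 falls back on an earlier non-missing value. Suppose Day 1 bicarbonate is '>40', Screening is in range and a later quantified value exceeds 32. The participant is then counted as shifting to high, although Day 1 was already beyond the limit.

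**The case against.** The best defence is that the NQ sentence concerns displays, while the next bullet defines a derived classification that turns on what participants reported. A programmer could take a received '>40' as such a report. This is possible but strained: Tables 3.11 and 3.13 are themselves summary displays, even with 'Summary/Listing' in their titles, and the NQ rule stands immediately above the classification without a carve-out.

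A second defence is that the results remain visible. This stands in part. NQ results are listed as received, for instance in the "Listing of Chemistry Data with Character Results" and its haematology counterpart, and the rule does not exclude them from the "Listing of Chemistry Values of Potential Clinical Importance". No record is lost, but the listings do not correct the table counts.

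A third is that Section 10.5.2 reports n as well as N for categorical data, so participants with no evaluable value may fall out of the denominator; the company table shell could settle this and is not shown. That weakens the point for a participant with only an off-scale result. It does not help one who also has a quantified in-range value.

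Some stronger readings are not supported:

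- A reader might infer that the error always understates PCI shifts. The baseline case above shows otherwise.
- A reader might add the five single liver tests and count 31 analytes. Sections 8.3, 10.8.1 and 10.10.5 treat liver tests separately, with their own PCI table and displays, and nothing places them in Tables 3.11 or 3.13.
- A reader might cite the ECG category 'Unable to evaluate' as a precedent. It applies "if all on-treatment assessments are" so rated; it is a recorded assessment outcome, not a category for missing data.
- A reader might extend the point to the maxima in Figures 3.2 and 3.3. The SAP leaves their NQ handling open, but no error is shown there.

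**Conclusion.** The point holds as a minor correction. Read literally, Section 10.6.4 can place a participant with a certain PCI value in the no-change category of Tables 3.11 and 3.13. Three conditions must hold together: an in-range baseline, no quantified on-treatment value beyond the same limit, and an off-scale bound at or beyond an existing limit.

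The reach is at most 26 analytes for '>x' and 21 for '<x'. How often it happens cannot be derived, because no assay limits are given, and the answer may be never. The 2.0 points per miscount assume the planned 50 per arm; early termination makes smaller arms, and so a larger weight, likely. The results are descriptive and the underlying records are kept, so the defect is confined to the summary counts.

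**What to change.** In Section 10.6.4, restrict NQ-as-missing to continuous summaries (n, mean, SD, median, minimum, maximum). For the worst-case PCI classification, at baseline as well as post-baseline, use the reported bound whenever it settles PCI status: '>x' with x at or above the upper limit is high, and '<x' with x at or below the lower limit is low. Where the bound does not settle the status and the participant has no other evaluable on-treatment value, footnote that participant as not classifiable instead of counting no change.

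The cost is one clause in the SAP, minor programming on data already held, and a footnote in Tables 3.11 and 3.13.
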